7.6.2. Secondary Efficacy Analyses

Secondary efficacy analyses will include the following treatment comparisons at the Week 25 visit using the ITT Analysis Set:

1. Mean change from baseline in range of motion of the affected joint, relative to a reference standard for the same joint (as defined below).²⁰
2. Proportion of responders based on centrally evaluated MRI scans and TVS.

3. Mean change from baseline score in the PROMIS Physical Function Scale.
4. Mean change from baseline score in the Worst Stiffness NRS item.
5. Proportion of responders based on BPI Worst Pain NRS item and analgesic use (BPI-30, as defined below).

The above-listed endpoints will be analyzed using a hierarchical (“gatekeeping”) testing procedure.³³ Thus, if the primary analysis of responder rate by RECIST 1.1 is statistically significant favoring pexidartinib ($p < 0.05$), then secondary endpoint #1 will be analyzed, also based on the use of a two-sided test at the $\alpha = 0.05$ level of significance. If secondary endpoint #1 is statistically significant ($p < 0.05$), then the testing procedure will proceed to secondary endpoint #2, and so on. If the test for a particular endpoint is not statistically significant, the inference for all subsequent endpoints in the hierarchy will not be performed.

For responder analysis based on the BPI Worst Pain NRS item and analgesic use, a BPI-30 responder will be defined as a subject who (i) experienced a decrease of at least 30% in the mean BPI Worst Pain NRS item and (ii) did not experience a 30% or greater increase in narcotic analgesic use, comparing data collected during a 7-day period prior to the current visit for responder assessment with baseline values collected prior to the first dose of study treatment. A decrease of at least 30% in BPI Worst Pain NRS item has been shown to be clinically meaningful in several therapeutic areas.^{34,35} Subjects who do not provide data for the endpoint will be considered to be non-responders. Definition for increase in analgesic use is outlined in Section 6.4.11. See SAP for further details.

The proportion of TVS responders (ie, those who achieve a CR or PR based on TVS criteria) at the Week 25 (Part 1 Completion) visit will be analyzed using the same methodology as that used for the primary efficacy endpoint (Section 7.6.1).

Other secondary endpoints will be analyzed using MMRM. The dependent variable will be the change from baseline. Each of these models will include fixed effects for treatment group, time point, treatment group-by-time interaction, stratification factor of US sites versus non-US sites, and the baseline value of the corresponding endpoint as well as the baseline-by-time interaction. An unstructured variance-covariance matrix will be used. Statistical comparisons between treatment groups will be made at the specified time point.

For the endpoint of range-of-motion, raw measurements of the affected joint will be performed using a goniometer and expressed in degrees (Section 6.4.4). The value for a given joint will be normalized to a reference standard, ie, full range-of-motion for the same joint, to provide a relative value. The reference standard will be derived from American Medical Association disability criteria²⁰ and are included in the SAP. The change from baseline in relative range-of-motion at the Week 13 and Week 25 visits will then be calculated. MMRM will be employed to analyze the change from baseline, and a statistical comparison between treatment groups will be made for the Week 25 visit. Joint type will also be properly accounted for in the model.

Duration of response will also be analyzed as a secondary endpoint and will be summarized for responders based on (i) RECIST 1.1 and (ii) TVS. Duration of response is defined from the date of the first recorded response to the first date of documented disease progression. For subjects who do not have radiologic progression, the date of the last MRI scan will be censored. The

Kaplan-Meier product limit method will be used to compute the estimate and 95% CI of the median and 25th and 75th percentiles. The number of responders, the number with subsequent disease progression, and the number with censored values will be displayed as well. Within the framework of Kaplan-Meier methodology, the estimates for proportions of responders with response durations longer than 3, 6, 12, 18, and 24 months will also be provided.

Duration of response will be summarized for responders in each of the following three groups:

- (A) Subjects randomized to receive pexidartinib in Part 1 using data from Part 1 and Part 2;
- (B) Subjects randomized to receive placebo in Part 1;
- (C) Subjects in Part 2 who were randomized to receive placebo in Part 1.

For Group A, tumor assessment data from both Part 1 and Part 2 will be combined, and the baseline assessment will be the one recorded at the Screening visit. For Group B, the duration of response will be censored at Week 25 visit if no disease progression was documented, with the screening assessment serving as baseline. For Group C, the tumor assessment data in Part 2 will be used, with the baseline assessment being the last one before the first dose of pexidartinib in Part 2.

For each of the above three groups, the percentage and 95% CI will be provided for the best overall response in the order of CR, PR, SD, PD, and “Inevaluable.”

The analyses for the primary efficacy endpoint and BPI Worst Pain NRS item associated endpoints will also be performed on the Per-protocol Analysis Set as a sensitivity analysis.

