These above-listed endpoints will be analyzed using a hierarchical (“gatekeeping”) testing procedure. Thus, if the primary analysis is statistically significant ($p < 0.05$), then secondary endpoint #1 will be analyzed, also based on the use of a two-sided test at the $\alpha = 0.05$ level of significance. If secondary endpoint #1 is statistically significant ($p < 0.05$), then the testing procedure will proceed to secondary endpoint #2, and so on. If the test for a particular endpoint is not statistically significant, the inference for all subsequent endpoints in the hierarchy will not be performed.

Duration of response will also be a secondary efficacy endpoint and will be summarized by treatment group using the Kaplan-Meier product limit approach. The estimate and 95% CI will be provided for the median and the 25th and 75th percentiles.

All secondary endpoints of mean changes at Week 25 will be analyzed using mixed models for repeated measurements. The dependent variable will be the change from baseline. Each of these models will include fixed effects for treatment group, time point, treatment group-by-time interaction, stratification factor of US sites versus non-US sites, and the baseline value of the corresponding endpoint as well as the baseline-by-time interaction. An unstructured variance-covariance matrix will be used. Statistical comparisons between groups will be made at the specified time point. For secondary endpoints #2 and #5, the proportions of responders in the two treatment groups will be compared using Fisher’s exact test.

Safety analyses will be performed on the Safety Analysis Set, and safety variables, including treatment-emergent adverse events, laboratory tests, vital signs, and ECGs, will be summarized.

Sample Size Evaluation — The assumed responder rates for the primary endpoint are 10% (placebo) and 35% (pexidartinib). Based on the use of a two-sided, two-sample comparison of proportions at the $\alpha = 0.05$ level of significance by Fisher’s exact test, a sample size of 126 ITT subjects (63 per arm) provides 90% power to detect this magnitude of difference.

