Selection of stiffness and physical functioning as secondary endpoints was also based on a review of the literature, discussions with four clinical experts, and input from subjects with PVNS or GCT-TS. Stiffness was mentioned by 16 of the 22 participants (73%), including those with upper- and lower-extremity tumors, and specific impacts on functioning were mentioned by all participants either in the context of associations with specific symptoms or as a result of limitations to range of motion due to the tumors (Plexxikon, data on file).

Specifically, the PROMIS Physical Functioning items and a Worst Stiffness NRS item were selected on the basis of (i) specific recommendations from the clinical experts and (ii) the

alignment of the concepts measured by these instruments with the symptom experiences reported by subjects with PVNS/ GCT-TS in the qualitative study.

The PROMIS Physical Functioning items address symptoms of immobility. The first scale is applicable to subjects with lower-extremity tumors, and the second scale applies to subjects with upper-extremity tumors. Since tumors can be found in either the upper or lower extremities, the PROMIS Physical Functioning items provide the opportunity to include measurement of both sites in a way that is not possible with other similar instruments (eg, the Western Ontario and McMaster Universities Osteoarthritis Index for PVNS and GCT-TS, which only measures functioning in the lower extremities).

Stiffness will be evaluated using a Worst Stiffness NRS item. Similar to the BPI Worst Pain item, the Worst Stiffness NRS item uses a 24-hour recall period. Subjects are asked to recall their worst stiffness at the site of their tumor in the past 24 hours. Like the BPI Worst Pain item, assessments can also be combined and summarized over a longer time period to yield more accurate estimates of subjects' experiences of stiffness for weekly periods.

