7. STATISTICAL METHODS

7.1. Randomization and Stratification

The randomization ratio for Part 1 of the study will be 1:1 for active (pexidartinib) versus placebo. Randomization will be stratified by US versus non-US sites and by upper extremity versus lower extremity involvement.

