7.6. Efficacy Analyses

7.6.1. Primary Efficacy Analysis

The primary efficacy endpoint is the proportion of subjects who achieve a CR or PR at the Week 25 Visit (Table 2.1) based on centrally read MRI scans and RECIST 1.1. The primary analysis will be completed using the ITT Analysis Set. The proportions in the two treatment groups will be compared using Fisher's exact test (two-sided) at the alpha = 0.05 level of significance. In addition, the two-sided 95% CI for the difference between the responder proportions in the two treatment groups will be provided, using the Wilson method.^{29,30}

As a supportive analysis, mid-p adjustment of Fisher's exact test will also be performed.^{31,32}

Additionally, as a sensitivity analysis, the Cochran-Mantel-Haenszel test will also be carried out with the strata of US and non-US sites.

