7.6.4. Subgroup Analyses

The primary endpoint and BPI Worst Pain NRS item will be also analyzed in the following subgroups of the ITT population:

- Subjects with disease located in large joints (shoulder, elbow, hip, or knee);
- Subjects with disease located in small joints (joints other than the shoulder, elbow, hip, or knee);
- Subjects with disease located in the knee;
- Subjects with GCT-TS type of TGCT;
- Subjects with PVNS type of TGCT;
- Subjects with lower extremity tumors;
- Subjects with upper extremity tumors;
- Subjects at US sites;
- Subjects at sites outside of the US;
- Subjects at sites in the EU region only.

In each subgroup defined above, the analysis will be carried out using the same type of methodology as described for the overall analysis of the corresponding endpoint. These results will be considered exploratory because of the multiplicity issue and also smaller sample sizes that cannot be pre-specified. For subgroups without an adequate number of subjects, the analysis will not be performed.

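### Extremity is a randomization stratum but is missing from the PROMIS and Worst Stiffness models and from the CMH sensitivity analysis, so those MMRM tests are mildly conservative if it is prognostic

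*Combined protocol and SAP*

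**What the plan says.** Section 7.1 names two strata: "Randomization will be stratified by US versus non-US sites and by upper extremity versus lower extremity involvement". Sections 3.1 and 6.3 and the synopsis say the same.

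The analysis text carries only one of them forward:

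- **MMRM (Section 7.6.2, repeated in the synopsis).** The fixed effects are itemised: treatment, time, treatment-by-time, the "stratification factor of US sites versus non-US sites, and the baseline value of the corresponding endpoint", and baseline-by-time. Extremity is not in the list.
- **Primary endpoint sensitivity analysis (Section 7.6.1).** "the Cochran-Mantel-Haenszel test will also be carried out with the strata of US and non-US sites".
- **TVS response (Section 7.6.2).** It "will be analyzed using the same methodology as that used for the primary efficacy endpoint", so it takes the same region-only CMH strata.
- **Range of motion (Section 7.6.2).** This model alone gets an anatomical term: "Joint type will also be properly accounted for in the model".
- **Subgroups (Section 7.6.4).** Upper and lower extremity are listed, but only for two endpoints: "The primary endpoint and BPI Worst Pain NRS item will be also analyzed in the following subgroups of the ITT population".

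For PROMIS, extremity also decides which form the subject completes (Section 2.2.2): "The first scale is applicable to subjects with lower-extremity tumors, and the second scale applies to subjects with upper-extremity tumors". Section 6.4.8.4 then pools the two forms in one analysis.

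No reason is given for keeping one randomization factor and dropping the other.

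**The concern.** Stratified randomization makes the arms more alike on the stratifying factor than chance alone would. If that factor also predicts the outcome, the treatment estimate varies less from trial to trial. A model without the factor does not register this. It leaves the between-stratum variation in the residual and reports a standard error that is too large. The estimate stays unbiased, and the test rejects less often than its nominal level.

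The possible loss falls on PROMIS and Worst Stiffness, the third and fourth secondary endpoints in a fixed sequence. A non-significant result at either one stops inference for everything after it, so power lost at step 3 also reaches steps 4 and 5.

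PROMIS gives the stronger reason to include the factor, because extremity determines the item set. Range of motion is largely covered by its joint-type term.

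**Working it through.** **1. The plan's own figure.** Section 7.12 gives 63 per arm, 10% versus 35% response, two-sided alpha 0.05 and 90% power by Fisher's exact test. Enumerating both binomial distributions gives 90.6% at 63 per arm (90.0% at 62). The stated power is met. The primary test uses neither stratum and nothing here changes it.

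**2. PROMIS item sets.** Counting item codes in Section 15.7, the lower-extremity form has 13 items and the upper form 11, with 9 in common. That leaves 13 − 9 = 4 lower-only items (PFA23, PFA21, PFA10, PFA3) and 11 − 9 = 2 upper-only items (PFB34, PFB28r1). The overlap is heavy. It supports including the factor but does not show that scores on the two forms are not comparable.

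**3. Size of the effect on the MMRM tests.** Let q be the share in the smaller extremity group and d the difference in Week 25 change between extremities, in residual SDs after baseline adjustment. The documents give neither, so both are assumptions: q from 10% to 50%, d from 0.2 to 0.8. With extremity balanced across arms:

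- SE ratio (omitted / included): k = √(1 + q(1 − q)d²)
- True two-sided size when omitted: 2[1 − Φ(1.96k)]

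For q = 20%, d = 0.5: k = √(1 + 0.16 × 0.25) = √1.04 = 1.020, and size = 2[1 − Φ(1.999)] = 4.6%.

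For q = 50%, d = 0.8: k = √(1 + 0.25 × 0.64) = √1.16 = 1.077, and size = 2[1 − Φ(2.111)] = 3.5%.

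A simulation agrees. It used 40,000 replicates per setting, 63 per arm, and a Week 25 ANCOVA on treatment, region and baseline, with and without extremity. The treatment effects of 0.5 and 0.58 SD are also assumed, because Section 7.12 powers only the primary endpoint.

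| q, d | SE ratio | Size, omitted | Power at 0.5 SD, omitted vs included | Power at 0.58 SD, omitted vs included |
|---|---|---|---|---|
| 10%, 0.2 | 1.0017 | 4.9% | 78.9 vs 79.0 | 89.3 vs 89.3 |
| 20%, 0.5 | 1.0191 | 4.6% | 78.2 vs 79.3 | 89.0 vs 89.6 |
| 50%, 0.8 | 1.0770 | 3.5% | 74.6 vs 79.4 | 86.8 vs 89.8 |

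At q = 20%, d = 0.3 the SE ratio is 1.0069.

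**4. Check with a repeated-measures model.** A three-visit MMRM (Weeks 9, 17 and 25) was simulated with unstructured covariance, complete data, permuted blocks of 4 within the four strata, and 8,000 runs per setting. Block size and correlations are assumptions. Two-sided size, omitted versus included:

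- q = 10%, d = 0.5: 4.6% vs 4.9%
- q = 20%, d = 0.5: 4.7% vs 5.0%
- q = 20%, d = 1: 3.3% vs 4.8%

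The Monte Carlo standard error is about 0.2 points. Adding extremity brings the size back to about 5%.

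**5. CMH sensitivity analysis.** At 10% versus 35% response and 20% upper extremity, with 200,000 replicates, power for region only versus region by extremity was:

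- extremity odds ratio 1: 93.5 vs 93.6
- odds ratio 2: 93.6 vs 93.9
- odds ratio 3: 93.8 vs 94.4

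The gain is 0.1 to 0.3 points at odds ratios 1 to 2.

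**The case against.** **The premise is not established.** Nothing in the documents shows that extremity predicts Week 25 change, and if it does not, omitting it loses nothing. The largest losses need an even extremity split and a 0.8 SD effect remaining after baseline adjustment. Section 1.3.1 reports the knee as the most common site in the Phase 1 cohort, which makes an even split less likely. This stands, and the moderate case is the one to weigh.

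**Much of the PROMIS concern is already handled.** The outcome is change from baseline, form is assigned by tumor location, and baseline and baseline-by-time are in the model. Worst Stiffness is one common item, so the form argument does not apply to it. This limits the likely size of d but does not explain why one randomization factor is in the model and the other is not.

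**The CMH change gains almost nothing and risks sparse strata.** Both are true. That part rests on consistency with the randomization, and it needs a pooling rule.

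**The gain is a best case.** A single time-constant extremity term does not fully capture an effect that grows over visits. With effects of 0, 0.25 and 0.5 SD at Weeks 9, 17 and 25, 20% upper extremity and correlation 0.6 (all assumed), about 0.5 of the original 2.0 percentage points of SE excess remains. The term therefore still removes (2.0 − 0.5)/2.0, about three quarters.

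**Model detail may be elsewhere.** The protocol refers to a SAP for further details, and no separate SAP model text was available for this check. The protocol nevertheless gives an explicit list of effects. If the SAP already names extremity, the two texts need reconciling.

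**Conclusion.** The point holds, as a modest matter of efficiency and consistency. Extremity is balanced by design and then left out of the PROMIS and Worst Stiffness MMRMs and the CMH strata. The only possible error is conservative; no false claim could result.

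Across the assumed range (10% to 50% in the smaller group, 0.2 to 0.8 SD):

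- the standard error is 0.2% to 7.7% too large;
- the true size is about 4.9% down to 3.5%;
- power falls by 0.1 to 3.0 points from about 90%, or by 0.1 to 4.8 points from about 79%.

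The moderate case (20%, 0.3 to 0.5 SD) costs 0.3 to 1.1 points. These figures assume 126 subjects and complete data; dropout related to extremity was not modelled. The change is worth making because it costs very little and the endpoints affected are gates in the hierarchy.

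**What to change.** - Add upper versus lower extremity, as randomized, as a fixed effect in the PROMIS and Worst Stiffness MMRMs. Add it to the range-of-motion MMRM too if the joint-type term does not already determine it. Otherwise state why it is omitted.
- Keep Fisher's exact test as the primary analysis.
- Run the existing CMH sensitivity analysis for the primary and TVS endpoints over region by extremity, with a pre-specified pooling rule. For example, if a stratum has fewer than 5 subjects in either arm, pool the two regions within that extremity.
- If Part 1 has already been unblinded, leave the pre-specified models in place and report the extremity-adjusted results as labelled sensitivity analyses.

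The cost is wording and one degree of freedom per MMRM; the factor is already recorded at randomization. The pooling rule is needed because, with an even region split, each arm has 63/2 = 31.5 subjects per region. At 10%, 20% or 30% upper extremity that leaves about 3, 6 or 9 upper-extremity subjects per arm per region, or about 0.3, 0.6 or 0.9 expected placebo responders at the 10% rate.

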7.6.3. Additional Efficacy Analyses

Additional efficacy endpoints to be analyzed at Week 25, with the exception of duration endpoints or otherwise indicated, include:

- Proportion of responders on the BPI Worst Pain NRS item and analgesic use by BPI-2p definition (see below)
- Proportion of responders on the BPI Worst Pain NRS item and analgesic use by BPI-50 (see below)
- Proportion of responders on the Worst Stiffness NRS item
- Proportion of responders on the PROMIS Physical Function Scale
- Mean change from baseline in the BPI Worst Pain NRS item
- Patient Global Impression of Change item for tumor-related stiffness and Patient Global Rating of Concept item for ability to carry out every day physical activities.
- Duration of BPI-based symptom response, analyzed for BPI-30, BPI-50 and BPI-2p.
- Results of the Surgical Assessment Questionnaire in Part 1.
- Response based on the change in the SSD of the tumor on MRI, referred to as “modified RECIST 1.1–SSD”

- Amount of joint/tissue damage (eg, bone erosion, bone edema, cartilage loss) assessed on MRI based on adaptations of the RAMRIS and WORMS
- Analgesic use expressed as morphine-equivalent doses in Part 1²²
- EQ-5D-5L parameters in Part 1
- Major HCRU and productivity in Part 1
- Duration of response based on MRI and modified RECIST 1.1-SSD
- Response based on the most disturbing symptom of pain, stiffness, or compromised ability to carry out everyday activities.
- Proportion of subjects receiving surgical resection of their tumor by 25 weeks, 49 weeks, 73 weeks, and 97 weeks of pexidartinib treatment

For responder analysis based on the BPI Worst Pain NRS item and analgesic use, a BPI-2p responder will be defined as a subject who (i) experienced a decrease of at least 2 points in the mean BPI Worst Pain NRS item and (ii) did not experience a 30% or greater increase in narcotic analgesic use, comparing data collected during a 7-day period prior to the current visit for responder assessment with baseline values collected prior to the first dose of study treatment. A BPI-50 will have the same definition except the subject must experience a decrease of at least 50% in the mean BPI Worst Pain NRS item. Subjects who do not provide data for the endpoint will be considered to be non-responders. Definition for increase in analgesic use is outlined in Section 6.4.11. See SAP for further details.

The endpoints involving the PRO assessments, amount of joint/tissue damage, response based on MRI and modified RECIST 1.1-SSD, and duration of response will be analyzed using the same methods as those used for the primary and secondary endpoints.

Duration of BPI symptom response for a responder is the interval from the first time BPI symptom response is documented to the first subsequent time point when the BPI symptom response is not met. The definition applies to BPI symptom response of BPI-30, BPI-50 and BPI-2p. Duration of BPI symptom response will be summarized in a way similar to that for duration of tumor response by RECIST 1.1.

For subjects who undergo surgical resection, the surgery-related data will be listed, including those collected in the separate protocol, if applicable. Proportion of subjects receiving surgical resection of their tumor by 25 weeks of pexidartinib treatment will be calculated regardless of whether blinded or open-label pexidartinib treatment, or both, was taken. The numerator is the number of subjects having the surgical resection of the tumor within 36 weeks of the first treatment of pexidartinib, taking into account the 12 weeks allowable window. The denominator is the number of subjects who complete at least 24 weeks of pexidartinib treatment. Likewise, the proportion of subjects receiving surgical resection of their tumor by 49 weeks, 73 weeks, and 97 weeks of pexidartinib treatment will be calculated similarly.

